13.5.2 Definition of SAEs

An SAE is defined as any AE that, at any dose, meets one of the following criteria:

- Results in death
- Is life-threatening
 - The term "life-threatening" in the definition of "serious" refers to an event in which the participant was at risk of death at the time of the event. It does not refer to an event that hypothetically might have caused death if it were more severe.

• Requires inpatient hospitalization or prolongation of existing hospitalization

- In general, hospitalization signifies that the participant has been admitted (usually involving at least an overnight stay) to the hospital or emergency ward for observation and/or treatment that would not have been appropriate in the physician's office or outpatient setting. Complications that occur during hospitalization are AEs. If a complication prolongs hospitalization or fulfills any other serious criteria, the event is serious. When in doubt as to whether hospitalization occurred or was necessary, the AE should be considered serious.
- Hospitalization for elective treatment of a pre-existing condition that did not worsen from baseline is not considered an AE.

• Results in persistent or significant disability/incapacity

- The term disability means a substantial disruption of a person's ability to conduct normal life functions.
- This definition is not intended to include experiences of relatively minor medical significance, such as uncomplicated headache, nausea, vomiting, diarrhea, influenza, and accidental trauma (eg, sprained ankle), that may interfere with or prevent everyday life functions but do not constitute a substantial disruption.

• Is a congenital anomaly/birth defect

- Other situations:
 - Medical or scientific judgment should be exercised by the investigator in deciding whether SAE reporting is appropriate in other situations, such as significant medical events that may jeopardize the participant or may require medical or surgical intervention to prevent one of the other outcomes listed in the above definition. These events should usually be considered serious.

13.5.3 Recording and Follow-up of AEs and/or SAEs

AE and SAE Recording

- When an AE/SAE occurs, the investigator is responsible for reviewing all documentation (eg, hospital progress notes, laboratory reports, and diagnostics reports) related to the event.
- The investigator will then record all relevant AE/SAE information.
- It is **not** acceptable for the investigator to proactively send photocopies of the participant's medical records, except an autopsy report in the event of death, to the sponsor's representative in lieu of completion of the required form.
- There may be instances when copies of medical records for certain cases are requested by the sponsor's representative. In this case, all participant identifiers, with the exception of the participant number, will be redacted on the copies of the medical records before submission to the sponsor's representative.
- The investigator will attempt to establish a diagnosis of the event based on signs, symptoms, and/or other clinical information. Whenever possible, the diagnosis (not the individual signs/symptoms) will be documented as the AE/SAE.

Assessment of Intensity

The investigator will make an assessment of intensity for each AE and SAE reported during the study and assign it to one of the following categories:

- Mild: An event that is easily tolerated by the participant, causes minimal discomfort, and does not interfere with everyday activities.
- Moderate: An event that causes sufficient discomfort to interfere with normal everyday activities.
- Severe: An event that prevents normal everyday activities. An AE that is assessed as severe should not be confused with an SAE. "Severe" is a category used for rating the intensity of an event; both AEs and SAEs can be assessed as severe.

An event is defined as "serious" when it meets at least 1 of the predefined outcomes described in the definition of an SAE, NOT when it is rated as severe.

Assessment of Causality

- The investigator is obligated to assess the relationship between study drug and each occurrence of an AE/SAE/AESI.
- A "reasonable possibility" of a relationship conveys that there are facts, evidence, and/or arguments to suggest a causal relationship, rather than that a relationship cannot be ruled out.
- The investigator will use clinical judgment to determine the relationship.
- Alternative causes, such as underlying disease(s), concomitant therapy, and other risk factors, as well as the temporal relationship of the event to study drug administration will be considered and investigated.
- The investigator will also consult the prescribing information, for marketed products, in their assessment.
- For each AE/SAE/AESI, the investigator must document in the medical notes that they have reviewed the AEs/SAEs/AESIs and have provided an assessment of causality.
- There may be situations in which an SAE has occurred and the investigator has minimal information to include in the initial report to the sponsor. However, it is very important that the investigator makes an assessment of causality for every event before initial transmission of the SAE data to the sponsor.
- The investigator may change their opinion of causality in light of follow-up information and send an SAE follow-up report with the updated causality assessment.
- The causality assessment is one of the criteria used when determining regulatory reporting requirements.

Follow-up of AEs and SAEs

- The investigator is obligated to perform or arrange for the conduct of supplemental measurements and/or evaluations as medically indicated or as requested by the sponsor's representative to elucidate the nature and/or causality of the AEs/SAEs/AESIs as fully as possible. This may include additional laboratory tests or investigations, histopathological examinations, or consultation with other health care professionals.
- If a participant dies during participation in the study or during a recognized follow-up period, the investigator will provide the sponsor with a copy of any post-mortem findings, including histopathology.
- New or updated information will be recorded in the originally submitted documents.
- The investigator will submit any updated SAE data to the sponsor or designee within 24 hours of receipt of the information.

13.5.4 Reporting of SAEs

SAE Reporting to the Sponsor via an EDC Tool

- The primary mechanism for reporting an SAE to the sponsor's representative (ie, PPD Pharmacovigilance) will be the EDC tool.
- If the electronic system is unavailable, then the site will use the paper SAE data collection tool (see the following section) to report the event within 24 hours.
- The site will enter the SAE data into the electronic system as soon as it becomes available.
- After the study is completed at a given site, the EDC tool will be taken off-line to prevent the entry of new data or changes to existing data.
- If a site receives a report of a new SAE from a study participant or receives updated data on a previously reported SAE after the EDC tool has been taken off-line, then the site can
report this information on a paper SAE form (see the following section) or to the sponsor's representative by phone.

• Contacts for SAE reporting can be found in the Investigator's Study File.

SAE Reporting to the Sponsor via Paper Data Collection Tool

- Facsimile transmission of the SAE paper data collection tool is the preferred method to transmit this information to the sponsor's representative.
- In the unlikely event of EDC downtime, the paper forms must be used for reporting of events that require expedited reporting (SAEs/AESIs). Paper forms should be faxed to PPD Pharmacovigilance at [name].
- Initial notification via fax does not replace the need for the investigator to complete and sign the SAE data collection tool within the designated reporting time frames.
- Contacts for SAE reporting can be found in the Investigator's Study File.

13.6 Appendix: Liver Safety

Abbreviations: AST, aspartate aminotransferase; ALT, alanine aminotransferase; CMV, cytomegalovirus; CPK, creatine phosphokinase; CRF, case report form; DNA, deoxyribonucleic acid; EBV, Epstein-Barr virus; HAV, hepatitis A virus; HBc, hepatitis B core; HBV, hepatitis B virus; HCV, hepatitis C virus;

Property of the Sanofi Group - strictly confidential

HEV, hepatitis E virus; IgM, immunoglobulin M; IMP, investigational medicinal product; INR, international normalized ratio; LFT, liver function test; LKM, liver-kidney microsome; PT, prothrombin time; RNA, ribonucleic acid; ULN, upper limit of normal.

*If unable to retest in 72 hours, use original laboratory results to decide on further reporting/monitoring/discontinuation.

Notes:

"Baseline" refers to ALT value at the baseline visit or, if the baseline value is unavailable, to the last ALT value before the baseline visit. The algorithm does not apply to instances of an increase in ALT during screening.

Section 13.5 provides guidance on safety reporting.

Normalization is defined as ≤ULN or baseline value, if the baseline value is >ULN.

13.7 Appendix: Contraceptive and Barrier Guidance DEFINITIONS

Woman of Childbearing Potential

- A woman is considered WOCBP (fertile) from the time of menarche until becoming postmenopausal (as follows) unless permanently sterile (as follows).
- A postmenopausal state is defined as the period of time after a woman has experienced no menses for 12 consecutive months without an alternative medical cause.
 - A high follicle-stimulating hormone (FSH) level in the postmenopausal range may be used to confirm a postmenopausal state in women not using hormonal contraception or hormonal replacement therapy (HRT).
 - Females on HRT and whose menopausal status is in doubt will be required to use one of the non-estrogen hormonal highly effective contraception methods if they wish to continue their HRT during the study. Otherwise, they must discontinue HRT to allow confirmation of postmenopausal status before study enrollment.

Permanent sterilization methods include the following:

- Documented hysterectomy.
- Documented bilateral salpingectomy.
- Documented bilateral oophorectomy.
- For individuals with permanent infertility due to a medical cause other than these procedures (eg, Mullerian agenesis, androgen insensitivity, gonadal dysgenesis), investigator discretion should be applied in determining study eligibility.

Note: Documentation can come from the site personnel's review of the participant's medical records, medical examination, or medical history interview.

If fertility is unclear (eg, amenorrhea in adolescents or athletes) and a menstrual cycle cannot be confirmed before first administration of study drug, additional evaluation should be considered.

Woman of Non-childbearing Potential

Women in the following categories are considered WONCBP:

- 1. Any female with permanent infertility due to one of the following:
 - Documented hysterectomy.
 - Documented bilateral salpingectomy.
 - Documented bilateral oophorectomy.
 - For individuals with permanent infertility due to a medical cause other than these procedures (eg, Mullerian agenesis, androgen insensitivity, gonadal dysgenesis), investigator discretion should be applied in determining study eligibility.
- 2. Postmenopausal female.

A postmenopausal state is defined as the period of time after a woman has experienced no menses for 12 consecutive months without an alternative medical cause.

- A high FSH level in the postmenopausal range may be used to confirm a postmenopausal state in women not using hormonal contraception or HRT.
- Females on HRT and whose menopausal status is in doubt must discontinue HRT to allow confirmation of postmenopausal status before study enrollment.

Note: Documentation can come from the site personnel's review of the participant's medical records, medical examination, or medical history interview.

Contraception Guidance

CONTRACEPTIVES^a ALLOWED DURING THE STUDY INCLUDE THE FOLLOWING:

Highly effective methods^b that have low user dependency

Failure rate of < 1% per year when used consistently and correctly.

- Implantable progestogen-only hormone contraception associated with inhibition of ovulation^c
- Intrauterine device (IUD)

CONTRACEPTIVES^a ALLOWED DURING THE STUDY INCLUDE THE FOLLOWING:

- Intrauterine hormone-releasing system (IUS)^c
- Bilateral tubal occlusion
- Azoospermic partner (vasectomized or due to a medical cause)

Azoospermia is a highly effective contraceptive method provided that the partner is the sole sexual partner of the WOCBP and the absence of sperm has been confirmed. If not, an additional highly effective method of contraception should be used.

Note: Documentation of azoospermia for a male participant can come from the site personnel's review of the participant's medical records, medical examination, or medical history interview.

Highly effective methods^b that are user dependent

Failure rate of < 1% per year when used consistently and correctly.

Combined (estrogen- and progestogen-containing) hormonal contraception associated with inhibition of ovulation^c

- Oral
- Intravaginal
- Transdermal
- Injectable

Progestogen-only hormone contraception associated with inhibition of ovulation^c

- Oral
- Injectable

Sexual Abstinence

Sexual abstinence is considered a highly effective method only if defined as refraining from heterosexual intercourse during the entire period of risk associated with the study drug. The reliability of sexual abstinence needs to be evaluated in relation to the duration of the study and the preferred and usual lifestyle of the participant.

CONTRACEPTIVES^a ALLOWED DURING THE STUDY INCLUDE THE FOLLOWING:

^a Contraceptive use by men or women should be consistent with local regulations regarding the use of contraceptive methods for those participating in clinical studies.

^b Failure rate of <1% per year when used consistently and correctly. Typical use failure rates differ from those when used consistently and correctly.

^c Male condoms must be used in addition to hormonal contraception.

Note: Periodic abstinence (calendar, symptothermal, post-ovulation methods), withdrawal (coitus interruptus), spermicides only, and the lactational amenorrhea method (LAM) are not acceptable methods of contraception for this study. Male condom and female condom should not be used together (due to risk of failure from friction).

Collection of Pregnancy Information

Male Participants With Partners Who Become Pregnant

- The investigator will attempt to collect pregnancy information on any male participant's female partner who becomes pregnant while the male participant is in this study. This applies only to male participants who receive Soliqua 100/33.
- After obtaining the necessary signed informed consent from the pregnant female partner directly, the investigator will record pregnancy information on the appropriate form and submit it to the sponsor or designee within 24 hours of learning of the partner's pregnancy. The female partner will also be followed up to determine the outcome of the pregnancy. Information on the status of the mother and child will be forwarded to the sponsor. Generally, the follow-up will be no longer than 6 to 8 weeks after the estimated delivery date. Any termination of the pregnancy will be reported regardless of fetal status (presence or absence of anomalies) or indication for the procedure.

Female Participants Who Become Pregnant

• The investigator will collect pregnancy information on any female participant who becomes pregnant while participating in this study. The initial information will be recorded on the appropriate form and submitted to the sponsor or designee within 24 hours of learning of a participant's pregnancy.

Property of the Sanofi Group - strictly confidential

- The participant will be followed up to determine the outcome of the pregnancy. The investigator will collect follow-up information on the participant and the neonate and the information will be forwarded to the sponsor. Generally, follow-up will not be required for longer than 6 to 8 weeks beyond the estimated delivery date. Any termination of pregnancy will be reported, regardless of fetal status (presence or absence of anomalies) or indication for the procedure.
- Although pregnancy itself is not considered to be an AE or SAE, any pregnancy complication or elective termination of a pregnancy for medical reasons will be reported as an AE or SAE.
- A spontaneous abortion (occurring at <22 weeks gestational age) or still birth (occurring at >22 weeks gestational age) is always considered to be an SAE and will be reported as such.
- Any poststudy pregnancy-related SAE considered reasonably related to the investigational product by the investigator will be reported to the sponsor as described in Section 6.3.5.5. Although the investigator is not obligated to actively seek this information for former study participants, they may learn of an SAE through spontaneous reporting.
- Any female participant who becomes pregnant while participating in the study will be discontinued from study drug treatment.

13.8 Appendix: Source Documents

Source documents provide evidence for the existence of the participant and substantiate the integrity of the data collected. Source documents are filed at the investigator's site.

Data entered in the eCRF that are transcribed from source documents must be consistent with the source documents or the discrepancies must be explained. The investigator may need to request previous medical records or transfer records, depending on the study. In addition, current medical records must be available.

DEFINITION OF SOURCE DATA

Source Data to Be Found in the Participant's File

Evaluations that are reported in the eCRF must be supported by appropriately signed, related, and identified source documentation that may include, but is not limited to, the following:

- Agreement and signature of ICFs (Section 9.3) with the study identification and any privacy forms.
- Study identification (name).
- Treatment kit number, dates of administration, and doses of Soliqua 100/33 administered.
- Medical, surgical, and diabetes history, including information on the following:
 - Demography, inclusion, and exclusion criteria.
 - History of alcohol consumption and smoking.
 - Comorbidities.
 - Last participation in a clinical study.
 - Contraception method for WOCBP.
 - Previous and concomitant medications, including treatment for diabetes mellitus.
 - Dates and times of visits and assessments, including examination results.

- Vital signs, height, body weight, and clinical laboratory reports.
- AEs and follow-up.
- In case of an SAE, the site should file in the source documents, at least, copies of the hospitalization reports and any relevant examination reports documenting follow-up of the SAE.
- Date of premature study discontinuation (if any) and reason.

Source documentation may be found in the following:

- Participant's identity (identification card or other verification document of participant identity).
- Medical history.
- Nursing notes.
- Physician's notes.
- Participant's eDiary.
- Glucometer.

Source Data Verification Requirements for Screen Failures

For screen failure participants, the following source data must be verified: participant's identification details, the informed consent signed by the participant, the study identification (name), dates of study visits, and the main reasons for screen failure.

The investigator must maintain accurate documentation (source data) that supports the information entered in the eCRF.

Study monitors will perform ongoing source data verification to confirm that data entered into the eCRF by authorized site personnel are accurate, complete, and verifiable from source documents; that the safety and rights of participants are being protected; and that the study is being conducted in accordance with the currently approved protocol and any other study agreements, ICH GCP, and all applicable regulatory requirements.

13.9 Appendix: Eligibility and Analysis Criteria for CGM Measurements Eligibility Criteria

- Participants with less than equivalent of 8 days of evaluable CGM data (not necessarily consecutive) of a 14-day period (eg, days of CGM device wear × % time CGM device active < 8) during the run-in period will be considered as screen failures (Section 6.2.1).
- During the run-in period, CGM device reinsertion will be allowed for participants who do not meet the equivalent of at least 8 days of evaluable CGM data (not necessarily consecutive) over a 14-day period as a result of premature sensor failure (eg, days of CGM device wear × % time CGM device active < 8; Table 13-3 and Figure 13–1).
- During the end of the treatment period, CGM device reinsertion will also be allowed for participants who do not meet the equivalent of at least 8 days of evaluable CGM data (not necessarily consecutive) over a 14-day period as a result of premature sensor failure (eg, days of CGM device wear × % time CGM device active < 8), if data can be captured during the 14-day end-of-treatment window (Table 13-3 and Figure 13–1).
- For participants who discontinue study treatment prematurely, the visit window can be extended by 14 days to collect the CGM data before they permanently discontinue the treatment.

No. of Days CGM Device Worn ^a	Time CGM Device Active (%) ^a	Equivalent Days	
8	100	8.00	
9	89	8.01	
10	80	8.00	
11	73	8.01	
12	67	8.04	
13	62	8.01	
14	57	7.98	

Table 13-3	Criteria	for CGN	I Device	Reinsertion
		IUI CUII.		ixemsei uon

Abbreviations: AGP, Ambulatory Glucose Profile; CGM, continuous glucose monitoring.

Note: Any combination of number of days of CGM device worn and % time CGM device is active that results in fewer than 8 equivalent days (defined as ineligibility) of evaluable CGM data will require device reinsertion. ^a AGP report.

Figure 13–1 Criteria for CGM Device Reinsertion

Abbreviation: CGM, continuous glucose monitoring.

Analysis Criteria

• Endpoint data will be included in the analysis if at least 10 out of 14 days (not necessarily consecutive) have at least ≥80% of evaluable CGM data per 24-hour period during the run-in period as well as the end of the treatment period (ie, from Weeks 14 to 16).

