6.2 Efficacy Assessments

6.2.1 CGM Measures

Blinded CGM will be performed for 14 continuous days during baseline (ie, from Visit 2 to Visit 3.1) and again for 14 days at the end of the treatment period (ie, from Visit 6 to Visit 7; Section 13.1). The baseline CGM measure will be captured before discontinuing the daily (oral or injectable) or weekly GLP-1 RA, DPP-4i, or down-titration of SU by 50%, and before initiation of Soliqua 100/33 treatment. The blinded CGM device (FreeStyle Libre Pro) will be applied to the back of the upper arm of the participant and activated at Visit 2 (ie, the run-in period). Participants will be required to wear the device continuously for 14 days for baseline CGM data collection, with device removal and data download on Day -1 at their next site visit during the baseline period (ie, Visit 3.1), after collection of C-peptide, insulin, and plasma glucose data from the MMTT. Downloaded CGM data will be reviewed by the investigator to determine the participants' study eligibility. (Note: During the run-in period, CGM device reinsertion will be allowed for participants who do not meet the equivalent of at least 8 days of evaluable CGM data [not necessarily consecutive] over a 14-day period as a result of premature sensor failure [eg, days of CGM device wear × % time CGM device active < 8].) Similarly, participants will be required to continuously wear the device for 14 days at the end of the treatment period from Weeks 14 to 16 (ie, Visit 6 to Visit 7) to collect CGM data, with device removal and data download on the fifteenth day after CGM placement (ie, Visit 7), after collection of only plasma glucose data from the MMTT. Downloaded CGM data will be verified by the investigator at the site to determine participants' study completion. During the end of the treatment period, CGM device reinsertion will also be allowed for participants who do not meet the equivalent of at least 8 days of evaluable CGM data (not necessarily consecutive) over a 14-day period as a result of premature sensor failure (eg, days of CGM device wear \times % time CGM device active < 8), if data can be captured during the 14-day end of treatment window. (Note: The minimum requirement for evaluable CGM data is if at least 10 out of 14 days [not necessarily consecutive] have at least \geq 80% of evaluable CGM data per 24-hour period during the run-in period as well as the end of the treatment period [ie, from Weeks 14 to 16]; Battelino et al 2020.) Criteria for CGM device reinsertion are provided in Table 6-1 and Figure 6-1. Any combination of number of days of CGM device worn and % time CGM device is active (Table 6-1) that results in fewer than 8 equivalent days (defined as ineligibility) of evaluable

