
CGM data will require device reinsertion. Eligibility and analysis criteria for CGM measures are provided in Section 13.9.

No. of Days CGM Device Worn ^a	Time CGM Device Active (%) ^a	Equivalent Days
8	100	8.00
9	89	8.01
10	80	8.00
11	73	8.01
12	67	8.04
13	62	8.01
14	57	7.98

Table 6-1Criteria for CGM Device Reinsertion

Abbreviations: AGP, Ambulatory Glucose Profile; CGM, continuous glucose monitoring. ^a AGP report.

Figure 6–1 Criteria for CGM Device Reinsertion

Abbreviation: CGM, continuous glucose monitoring.

Participants with less than equivalent of 8 days of evaluable CGM data (not necessarily consecutive) of a 14-day period (eg, days of CGM device wear \times % time CGM device active < 8) during the run-in period will be considered as screen failures. For participants

Sanofi	SOLIQUA TM 100/33
Protocol: LPS16990 (Original, Version 1.0)	18 Aug 2021

who discontinue study treatment prematurely, the visit window can be extended by 14 days to collect the CGM data before they permanently discontinue the treatment.

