8.4 Analysis Sets

The following analysis sets will be used in the statistical analyses:

- Enrolled set: All eligible participants who are dispensed Soliqua 100/33 and sign the ICF.
- Efficacy analysis set: All enrolled participants who receive ≥1 dose of Soliqua 100/33 and have evaluable CGM data at baseline.
- Safety set: All enrolled participants who receive ≥ 1 dose of Soliqua 100/33.

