8.7.2 Analysis of Primary Endpoint

8.7.2.1 Main Estimation of Primary Estimand

The primary endpoint is to demonstrate the improvement from baseline in the percentage of TIR of 70 to 180 mg/dL during the last 2 weeks of treatment (Weeks 15 and 16) for the entire study population. The percentage of time spent in the glycemic target range will be calculated as 100 times the number of recorded measurements in the glycemic target range, (70-180 mg/dL) inclusive, divided by the total number of recorded measurements.

As described in Table 8-2, the mean and its associated 95% CI will be used to describe the changes in TIR (70-180 mg/dL) at Week 16 from baseline. A one-sample t-test will be applied to test the significance of changes. A p-value <0.05 will be considered significant.

As part of the definition for the efficacy analysis set, evaluable data (ie, not missing) is defined as the availability of at least 10 out of 14 days (not necessarily consecutive) with at least \geq 80% of evaluable CGM data per 24-hour period during the run-in period as well as the end of the treatment period (ie, from Weeks 14 to 16; Section 13.9), otherwise it will be considered as missing.

The primary estimand will be estimated based on the efficacy analysis set using obtained measurements, regardless of intercurrent events. Table 8-2 provides more details regarding the missing data definition.

The missing data related to the primary estimand due to lost-to-follow-up or treatment discontinuation will be imputed with their baseline observation carry forward (BOCF). Missing data due to technical issues of CGM devices will not be imputed. Details of handling missing data are provided in Section 8.7.3.3.

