data will be downloaded on the fifteenth day after CGM placement (ie, Visit 7; after collection of only plasma glucose data from the MMTT). Downloaded CGM data will be verified by the investigator at the site to determine participants' study completion.

r Participants who do not meet CGM compliance criteria at baseline will be considered screen failures.

s Participants will undergo the MMTT to assess maximum PPG exposure in the 4-hour period after the breakfast meal with biomarkers of β -cell function (plasma glucose, insulin, and C-peptide) measured at Visit 3.1 (ie, site visit during the baseline period), whereas only plasma glucose will be assessed at Visit 7 (ie, end of the treatment period).

t Participants should discontinue GLP-1RA, DPP-4i, or down-titrate SU medications after all baseline assessments have been completed. SU doses should be down-titrated by 50% when starting Soliqua 100/33, whereas the last dose of daily DPP-4i and daily GLP-1RA (oral or injectable) should be administered on the morning of Day -1, the day before the first dose of Soliqua 100/33.

Participants on weekly GLP-1RA should administer their last dose 7 (\pm 2) days before the first dose of Soliqua 100/33.

u Soliqua pen instructions will be given to all participants at Visit 3.1. A phone contact should be made to **participants on weekly GLP-1RA** on the day **before Soliqua 100/33 initiation**, to remind them of the next morning's injection and to provide instructions for SoloStar pen use.

v For the scheduled site visits, participants are required to arrive fasting without administering the Soliqua 100/33 injection. Fasting is defined as no food intake in the 8 hours before blood sampling, except water.

w Baseline DM-SAT should be completed before discontinuation or down-titration of baseline therapies. The questionnaire should be completed at the start of the visit before any other study tests or procedures are performed or Soliqua 100/33 is administered.

x The following hypoglycemia categories of interest will be presented: overall hypoglycemia and confirmed hypoglycemia (ADA Levels 1, 2, and 3; Section 6.3.2).

y Urinalysis: pH, glucose, ketones, leukocytes, blood/Hb, protein.

z Only for women of childbearing potential; urine pregnancy test.

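### Sites judge CGM eligibility and reinsertion on 8 equivalent days, but analysis requires complete individual days, so a participant can pass the site check, be dosed and fall outside the main CGM analysis

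*Protocol*

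**What the plan says.** **Site rule (protocol 4.2 criterion 4, 6.2.1, Tables 6-1 and 13-3, 13.9).** The screen-failure rule in 13.9 applies to "Participants with less than equivalent of 8 days of evaluable CGM data (not necessarily consecutive) of a 14-day period", computed as days worn times percentage of time active. The note to Table 13-3 says that any combination "that results in fewer than 8 equivalent days (defined as ineligibility) of evaluable CGM data will require device reinsertion". Neither rule looks at how complete a single day is.

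**Protocol analysis rule (6.2.1, 8.7.2.1, 13.9).** Section 6.2.1 also says "The minimum requirement for evaluable CGM data is if at least 10 out of 14 days", each at 80% or more, at run-in and again at Weeks 14 to 16. Section 13.9 repeats this as an inclusion rule for endpoint data: "Endpoint data will be included in the analysis if at least 10 out of 14 days" meet it. The efficacy analysis set (8.4) takes dosed participants who received drug "and have evaluable CGM data at baseline", and 8.7.2.1 defines evaluable by the same 10-day test. Section 8.7.3.3 treats data that are not evaluable as a technical problem and excludes the participant as missing completely at random.

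**SAP rule (Table 4, 4.3.1).** Compliance is met by 8 days at 100%, or 9 days at 89% or more, or 10 days at 80% or more. Section 4.3.1 adds a total of 768 records on those days. Only days with at least 80% of readings are analysed.

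**SAP on reinsertion and screen failure (1.1, 4.3.1, schedule footnotes o and r).** Reinsertion is allowed when SAP compliance is not met. Footnote r reads: "Participants who do not meet CGM compliance criteria at baseline will be considered screen failures".

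The SAP was approved on 28-Apr-2023; the first participant was enrolled on 27 January 2022. SAP 5.5 lists the compliance change, while SAP 5.2 states that protocol-planned analyses are unchanged.

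**The concern.** The rule that decides whether a participant is dosed or given a second sensor measures something different from the rule that decides whether the data count. A total of 8 equivalent days can be built from days that are too few, or each too incomplete, for analysis.

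Under the protocol as written, such a participant passes the check at Visit 3.1, receives study drug and is then excluded from the primary analysis. The same mismatch at Weeks 14 to 16 means that a second sensor, which the protocol already permits, is not called for. The stakes are avoidable exposure of people who cannot contribute to the primary question, some loss of evaluable participants, and site instructions that differ between the two documents.

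**Working it through.** **The plan's own figure.** Inputs from protocol 8.3: difference 10, SD 25, two-sided 0.05, power 95%, 15% loss.

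- Normal approximation: n = (25 × (1.960 + 1.645) / 10)² = 81.2, so 82. This reproduces the plan.
- One-sample t-test (noncentral t) at n = 82: power 94.7%.
- Completers: 100 × 0.85 = 85, t-test power 95.4%. The margin over 82 is 3, or 3/85 = 3.5% of completers.

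**Table rows against each rule.** Equivalent days = days worn × % active / 100. Readings = equivalent days × 96 (one per 15 minutes). The last two columns assume readings spread evenly over the worn days.

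| Row | Equivalent days | Readings | Site check | Protocol: 10 days at ≥80% | SAP compliance |
|---|---|---|---|---|---|
| 8 × 100% | 8.00 | 768 | pass | fail | pass |
| 9 × 89% | 8.01 | 769 | pass | fail | pass |
| 10 × 80% | 8.00 | 768 | pass | pass | pass |
| 11 × 73% | 8.03 | 771 | pass | fail | fail |
| 12 × 67% | 8.04 | 772 | pass | fail | fail |
| 13 × 62% | 8.06 | 774 | pass | fail | fail |
| 14 × 57% | 7.98 | 766 | reinsertion | n/a | n/a |

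**How far this depends on even spread.**

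- 8 × 100% and 9 × 89% need no assumption under the protocol rule: 8 or 9 worn days cannot contain 10.
- 11-, 12- and 13-day rows, protocol rule: ten days at 80% need 10 × 77 = 770 readings. These rows hold 771 to 774, so they pass only if nearly every reading falls on exactly ten days.
- The same rows, SAP rule: 768 readings must lie within 8, 9 or 10 days. That leaves about 3, 4 and 6 readings for all other worn days. A sensor that runs fully for 8 days and then stops passes (8 × 96 = 768); gaps spread over the worn days fail.
- 10 × 80% passes only if each of the ten days reaches 80%.

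**The gap is not confined to the threshold.** A 14-day wear at 79% on every day gives 14 × 0.79 = 11.06 equivalent days, well clear of reinsertion, yet has no day at 80%. Constructed extremes: 9 full days plus 5 days of 76 readings is 1244 of 1344 readings (92.6%) and still fails the protocol rule. Seven days of 96, one of 95, one of 84 and five of 76 is 1231 of 1344 (91.6%) and fails all three SAP options.

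**Effect on power.** The documents give no loss rate. Assumption: 5 to 10 of 85 completers are lost to the mismatch.

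- 85 − 5 = 80: t-test power 94.2%.
- 85 − 10 = 75: t-test power 92.8%.
- Against 94.7% at n = 82 by the same method, the reduction is about 0.5 to 2 percentage points.

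This counts the 15% who discontinue as lost, as the sample-size text does. The main analysis would impute them with the baseline value.

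**The case against.** The strongest reply is that 13.9 labels eligibility criteria and analysis criteria separately, so two tiers look intended, and that the SAP has largely repaired the difference. Its total of 768 records is exactly 8 × 96. It admits the 8- and 9-day patterns, it ties reinsertion to compliance, and SAP 5.5 declares the change with its reason. The failure the documents name is premature sensor failure, which suggests full days followed by none; under the SAP that pattern passes.

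Much of this stands, and it rules out several stronger readings that a reader might infer.

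- **Six of seven rows fail the protocol rule and four of seven the SAP rule.** The 14 × 57% row gives 7.98 and already requires reinsertion. Rows are also threshold combinations, so their count says nothing about how many participants are affected.
- **The second sensor is never triggered.** That is true of the protocol's rule, but SAP 1.1, 4.3.1 and footnote o allow reinsertion for non-compliance.
- **These participants are unanalysable.** They remain in the safety set and can enter the enrolled-set analyses of meal-test glucose, HbA1c and treatment satisfaction. A Week 16 failure enters the first sensitivity analysis by BOCF (SAP 4.3.3). Only a baseline failure leaves the efficacy set.
- **The printed equivalent days are wrong.** The table shows 8.01 where the products above give 8.03 and 8.06. Rounding of the displayed percentages accounts for this, and no decision changes.

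The reply does not remove the core problem. The SAP came 15 months after first enrolment, the protocol supplied still carries the 8-equivalent-day rule, and wear with dispersed gaps fails both analysis rules.

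**Conclusion.** The point holds. Of the six table rows that pass the site check, five can fail the protocol's analysis rule, two of them with certainty. Three of the six still fail the SAP rule if gaps are spread over the worn days. The protocol and SAP also disagree on who is a screen failure and when a sensor is replaced.

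The documents do not support a claim of serious lost power. The frequency is unknown, and on the assumed 5 to 10 of 85 completers power stays at 92.8% or above. The case for change rests mainly on dosing people whose CGM data cannot enter the primary analysis, and on conflicting instructions to sites.

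**What to change.** Use one day-level rule, the SAP compliance rule, for eligibility, reinsertion and analysis. Put it in protocol 4.2 criterion 4, 6.2.1, Tables 6-1 and 13-3, and 13.9, and remove the 11- to 14-day rows. SAP 4.3.1 ties reinsertion to premature sensor failure, so the new wording should say whether other gaps also qualify.

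If enrolment is over, report separately for run-in and Weeks 14 to 16 how many participants passed the site rule but failed the analysis rule. Correct SAP 5.2 so that it agrees with SAP 5.5.

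The cost is more than wording. Sites now read days worn and percentage active from the AGP report; they would need a record count for each 24-hour day, taken from the download they already review. A few more reinsertions or run-in screen failures should be expected. At Week 16 the rescue stays partial, because the protocol allows reinsertion only if data can still be captured within the 14-day end-of-treatment window.
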